## 2.3 Objectives

Objective 1. To assess the effect of early continuous skin-to-skin contact on survival of pre-stabilised preterm neonates <2000g

Objective 2. To assess the effect of early continuous skin-to-skin contact on other important clinical outcomes (growth, late onset infection and duration of hospital stay) for pre-stabilised neonates <2000g

Objective 3. To assess the safety of providing early continuous skin-to-skin contact to pre-stabilised neonates <2000g

Objective 4. To explore early and late mechanistic pathways for the beneficial effects of early continuous skin-to-skin contact compared to standard care in pre-stabilised neonates <2000g

## 3. Study methods

### 3.1. Trial design

This individually randomised, controlled, superiority trial compared 2 parallel groups of hospitalised, pre-stabilised neonates <2000g receiving either early continuous skin-to-skin contact (KMC started at <24h since admission) (intervention group) or standard care (KMC started at >24h since admission and once stable) (control group) (ratio 1:1). The intervention was un-blinded to participants and researchers. Primary outcome was all-cause mortality at 28d. The trial was conducted at the neonatal unit of the national teaching hospital (Edward Francis Small Teaching Hospital) in The Gambia from May 2018 to April 2020.

#### 3.1.1. Eligibility criteria

##### Inclusion criteria:

- New admission to the neonatal unit at EFSTH during the study period
- Admission weight less than 2000g
- Age 1 – 24h at time screening begins
- Alive at time of enrolment
- Singleton or completed twin birth admission
- Written informed consent provided by a parent/caregiver willing to provide the intervention

##### Exclusion criteria:

- Congenital malformation which is incompatible with life or requires immediate surgical correction
- Severe jaundice needing immediate management
- Seizures
- Clinically stable as assessed over a pre-defined period of cardio-respiratory monitoring
- Severely unstable as assessed over a pre-defined period of cardio-respiratory monitoring
- Completed triplet admission
- Mother and/or neonate already enrolled into another MRCG study at time of hospital admission

- No study bed available

### *3.1.2. Intervention procedures*

Participants in the intervention arm commenced the continuous skin-to-skin contact aspect of KMC within 24h after admission, aiming for >18h/day. It was provided by the first available caregiver (mother, father or other relative) in the trial area of the study site at the same time as any other medical or nursing care required by the neonate (E.g. oxygen, intravenous fluids, antibiotics, gastric feeds). Clear stopping criteria were in place for when to stop KMC due to clinical reasons. Skin-to-skin contact was re-commenced when stability criteria were met, as per the control arm.

### *3.1.3. Control procedures*

Participants were managed in an incubator or under a radiant heater, naked except for a woollen hat and nappy or wrapped in a cloth. The parent/caregiver could touch, hold, and feed the neonate as per standard practice but KMC was not provided until stability criteria were met and at greater than 24h since hospital admission. Participants received intermittent KMC in the trial area and continuous KMC was started after transfer to the adjacent KMC unit.

### *3.1.4. Procedures for both arms*

A pragmatic study design was used with a standardised preterm/LBW clinical management protocol based on current standard care. All management was provided by study site staff in collaboration with research clinicians with compliance to the management protocol monitored daily.

## **3.2 Randomisation & allocation**

An independent statistician generated a randomisation sequence using VBA (Visual Basic Application) within an Access database to produce two random number tables with stratification by admission weight categories (<1200g; ≥1200g). Random permuted blocks of varying sizes were used with 1:1 allocation. Allocation concealment was performed with sequentially numbered, opaque, sealed envelopes prepared by an independent researcher and accessible to study team only. Following collection of baseline data, the study nurse opened the next numbered envelope for the correct weight category. The participant identifier, date and time were recorded on the outside of the envelope prior to opening, to identify any subversion of allocation sequence. Twins were allocated to the same arm, according to the first eligible twin's weight.

## **3.3 Sample size**

A total of 392 participants (1:1 ratio) were required to detect a 30% relative reduction in the primary outcome (power 80%, alpha=0.05). This is based on an expected mortality rate of 48%, which was adjusted from observed rates of 56% to account for 15% mortality reduction due to trial implementation. Loss to follow up rates were low (<2%) due to the restricted geographical area, co-ordination of follow-up with routine appointments and re-imbursement of travel expenses.

### 3.4 Statistical interim analyses and stopping guidance

An un-blinded interim analysis was conducted by the DSMB in December 2019, once 50% of the intended sample size (n=196) were recruited and followed-up. The interim analysis included consideration of primary and secondary outcomes with the exception of intestinal carriage of ESBL-producing *Klebsiella pneumoniae*. Stopping rules for efficacy were pre-defined by the DSMB using the Haybittle-Peto rule and there was no adjustment of significance levels following the interim analysis. The DSMB recommended that the trial continue with no protocol changes.

### 3.5 Timing of final analysis

Data cleaning and data locking were performed once the final participant recruited during the study period completed follow up. All outcomes will be analysed at the same time, with the exception of secondary outcome “Intestinal carriage of ESBL *Klebsiella pneumoniae*” which may be performed at a later date, dependent on funding.

The statistical analysis plan will be added to the study protocol at [clinicaltrials.gov](https://clinicaltrials.gov) before closure of the database and before any analyses are conducted.

### 3.6 Timing of outcome assessments

Outcomes are assessed according to the following schedule:

Timing	Outcome
24h after study participation	

Cardio-respiratory stability (Mean adjusted SCRIp score)

Hypothermia (Prevalence of participants with temperature <36.5°C)

Daily whilst admitted to neonatal unit Weekly (day 7, 14, 21, 28) whilst admitted to KMC unit Ad-hoc reviews in event of clinical deterioration	

Time from start of study procedures to death (hours)

Incidence of clinically suspected infection from 3 – 28 days of age or latest follow-up

Day of discharge	

Exclusive breastfeeding

Duration of admission

Age 28 +/- 5 days	

Survival status (alive / died)

Weight gain (mean weight gain in g/day from baseline)

Prevalence of participants with intestinal carriage of ESBL-Klebsiella pneumoniae

## 4. Statistical principles

### 4.1 Confidence intervals (CIs) & P values

We consider P values <0.05 as statistically significant evidence of a difference between arms for all pre-specified outcomes. Results will be presented with 95% CIs.

### 4.2 Multiplicity

No adjustments for multiple statistical tests will be made.

### 4.3 Analysis populations

Analysis of primary and secondary outcomes will be conducted on an intention-to-treat basis for all enrolled participants. A sensitivity analysis will be performed excluding any participants

who were recruited in error and did not meet the eligibility criteria as stated in the most recent trial protocol.

#### **4.4 Adherence and protocol deviations**

##### *4.4.1 Adherence to the intervention*

Adherence to the intervention was monitored by direct observation of time a participant spent in KMC position and was manually recorded on paper CRFS by trial personnel. The following variables were recorded: date and time of first KMC contact; relationship of person providing KMC to participant; frequency and duration of each KMC session; number of neonates receiving KMC during each session and reason for stopping KMC session. The raw data were manually inputted to Excel and the total daily dose (from start of study procedures) of KMC received was automatically calculated before being reconciled with the trial database for every in-patient day. The average daily dose of in-patient KMC per duration of admission was automatically calculated in REDCap for each participant.

##### *4.4.2 Definition of protocol deviation*

A major protocol deviation is defined as a departure from the Trial Protocol or ICH-GCP standards which had an impact on the conduct of the study, the credibility of the data or safety of participants. This includes recruitment of an ineligible neonate, recruitment without consent or use of impartial witnesses; participants in the control arm receiving the intervention inappropriately or any deviation that resulted in a Serious Adverse Event (SAE, see section 6.5). Major deviations were reported to the sponsors and SCC / ethics committees within 5 working days, as per MRCG SOPs.

All other deviations from the study protocol or GCP standards were considered to be minor and were reported to the monitors on a monthly basis and the ethics committees on an annual basis. Only major protocol deviations will be summarised and reported in any publication of trial results.

### **5. Study population**

#### **5.1 Screening data**

The total number of neonatal admissions and proportion of those weighing  $\leq 2000\text{g}$  was prospectively recorded and will be presented as part of a separate survival analysis comparing mortality before and during the trial. Clinically eligible neonates who were not recruited will be compared with recruited neonates to compare general characteristics (age at admission, sex, referral status (inborn/outborn), stability at first screening) and outcomes (in-hospital mortality).

#### **5.2 Eligibility**

Eligibility was assessed in all neonates with referral weight  $\leq 2000\text{g}$  as soon as possible after admission and once aged  $>1\text{h}$  old. Weight was confirmed using calibrated SECA™ 757 digital weighing scale and source documents were checked for age and other study involvement. All potentially eligible neonates aged  $<24\text{h}$  underwent an examination with cardio-respiratory stability assessed over 10-minutes using Nonin™ 2500A pulse oximeter.

Inclusion criteria:

[figure not shown]
- New admission of singleton or twin
- Weight <2000g as per study scale
- Aged 1 - 24h old when screening begins
- Mother or other caregiver available and willing to provide intervention

Exclusion criteria:

- Triplets who were all admitted to study site
- Congenital malformation not compatible with life or needing immediate surgical intervention
- Severe jaundice
- Seizures
- Stable as assessed during cardio-respiratory screening
- Severely unstable as assessed during cardio-respiratory screening or died during screening
- No study bed available
- Neonates/mothers enrolled in another research study
- No written informed consent from parent or caregiver within 24h of admission

### 5.3 Recruitment

The number and flow of subjects through screening, randomisation, allocation, follow-up, and analysis will be documented, as per CONSORT 2010 guidelines. Reasons for exclusion, withdrawal and non-analysis will be described (Fig.1).

**Figure 1. Trial flow diagram, as per CONSORT guidelines 2010**

**5.4 Withdrawal / follow-up**

The number and proportion of participants who permanently withdrew from the study will be described with reasons for withdrawal. The proportion of participants who complete follow-up at 28+/-5 days will be described. Participants who are permanently withdrawn or lost to follow-up will be included in the analysis using data collected up-to the point that they are lost or withdrawn. An exception to this is if a participant withdraws and requests for no data to be used during analysis.

**5.5 Baseline patient characteristics**

Baseline socio-demographic and clinical characteristics of the neonate, mother and perinatal period will be summarised for each arm by number and proportion (categorical variables) and either means with standard deviations or medians and interquartile ranges, as appropriate (continuous variables). This will include comparison of treatments received prior to enrolment. Statistical tests of differences in baseline characteristics will not be performed.

**5.6 Adherence to the Standardised Preterm Management Protocol**

Compliance to the standardised preterm/LBW management protocol was monitored daily by the field team and key indicators of standard hospital management were recorded as concomitant medications (E.g. antibiotic therapy, provision of caffeine citrate or aminophylline to prevent apnoea of prematurity). Indicators will be compared between arms from time of study enrolment to discharge or death and will include receipt of key management and investigations. Characteristics will be descriptively summarised with categorical data presented using counts and percentages and continuous data presented using number of patients, mean, median, standard deviation, minimum, maximum and IQR, as appropriate. Data will be presented in the form of a table with arm-specific and total data. Statistical tests comparing concomitant treatments between both arms will be conducted, using Fishers exact tests for categorical variables and two sample *t* test for continuous variables to calculate p values with 95% CIs.

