#### *Kangaroo mother care is an evidence-based intervention for preterm/LBW hospitalised babies*

Kangaroo mother care (KMC) is recommended as standard care for all *stable*, hospitalised babies <2000g. It was developed in Colombia four decades ago and since adopted in both HIC and LMIC as an adjunct to incubator care. KMC is a complex intervention with the key component prolonged, continuous skin-to-skin contact between the nearly naked baby and mother's chest. The full definition, as described by Charpak et al, also includes promotion of early and exclusive breast-milk feeding, early discharge and close follow-up. Although other caregivers can provide skin-to-skin contact, a key aspect of KMC is the stimulation of maternal breast milk production and subsequent effects on feeding and growth.

Skin-to-skin contact and KMC are often used as synonyms in the literature, but for the purposes of this trial, early continuous skin-to-skin contact is considered the intervention under study.

Clinical benefits of KMC include reduced risk of: nosocomial infection; hypothermia, hypoglycaemia, severe infection and illness with moderate evidence of increased weight, length and head circumference gain and improved exclusive breast feeding at discharge, term and latest follow-up in *stable* neonates weighing less than 2000g. KMC also reduces duration of hospitalisation and hospital re-admission which benefits both neonate, mother and health care system. According to several systematic reviews, continuous KMC (>18h/day) reduces mortality by 36 - 51% compared to conventional incubator care. The most recent Cochrane review (2016) reported a 40% reduced risk of mortality at discharge or 40-41 weeks postmenstrual age (RR 0.60, CI 0.39-0.92; 8 trials, 1736 infants) and latest follow-up (RR 0.67, CI 0.48-0.85). However, this mortality effect is for "stable" neonates <2000g and there is an evidence gap for the mortality-effect of KMC in unstable babies within 24h after birth, when preterm/LBW babies undergo a physiological transition from in-utero to ex-utero life and are at greatest risk of mortality or near death events such as apnoea, hypoxia and bradycardia.

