### *Feasibility study to inform planning of eKMC*

From April to August 2017, a prospective observational feasibility study was conducted at the study site with the aims of understanding the target population and assessing the feasibility of conducting the clinical trial. From this data and previous published audit data from the study site, the clinical trial is considered feasible with an estimated 245 clinically eligible patients admitted per year. Barriers to recruitment are absence of caregiver within 24h of admission (21%), death or severe instability during screening period (23%) and consent refusal (14%). Mortality in eligible subjects at 28d is 56% (14/25) with median age at time of death 3d 2h and 71% (10/14) of all deaths occurred within the first week of admission. The feasibility study also identified key enablers and barriers to the provision of early KMC. These included maternal willingness to practice continuous KMC with good family support and the need for enhanced education of both health care workers and parents about providing early KMC alongside other medical interventions. These results will inform the sensitisation, planning and conduct of the clinical study.

References of literature and data are listed in Section 18.

Protocol #: 1

---

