## 3.5 Concomitant medications/treatments

All other medicines and treatments will be prospectively recorded on the hospital medical record and electronic CRF (eCRF). They will be provided to the participant as per a standardised preterm/LBW management protocol, based on current standard care and guidelines at the study site. The protocol will include details on routine stabilisation, fluids, feeding and respiratory management; complications of prematurity/LBW (hypoglycaemia, jaundice etc); medications, investigations and discharge / transfer and follow-up criteria.

The protocol will be based on a combination of direct observation, available guidelines and will be developed in collaboration with the medical team at EFSTH. Compliance with WHO guidelines will be encouraged, where possible. Compliance to the standardised preterm/LBW management protocol will be monitored regularly through-out the study and also analysed for any significant differences in key indicators at the end of the study. Any obvious discrepancies in treatment between the two arms will be identified prospectively and actions taken to ensure that both arms receive the same medical and nursing treatment.

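### SAP 5.6 tests receipt of other care over a window closed by death or discharge, so later-accruing care can look unequal between arms when it was delivered identically

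*SAP*

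**What the plan says.** SAP 5.6 (Adherence to the Standardised Preterm Management Protocol) sets the window: "Indicators will be compared between arms from time of study enrolment to discharge or death and will include receipt of key management and investigations".

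The summary form is stated: "Characteristics will be descriptively summarised with categorical data presented using counts and percentages". So is the test: "Statistical tests comparing concomitant treatments between both arms will be conducted, using Fishers exact tests for categorical variables", with a two-sample t test for continuous variables. The section names no common window, no per-day denominator and no handling of death or discharge.

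Protocol 3.5 gives the purpose. Compliance with the management protocol is to be monitored during the trial and "also analysed for any significant differences in key indicators at the end of the study".

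Two neighbouring parts of the SAP do allow for time. Section 5.7 reports KMC dose over the first 7 days and per day admitted, and section 6.2 allows person time as a denominator for secondary outcomes. Neither provision extends to 5.6.

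**The concern.** The length of the window is itself affected by allocation. All-cause mortality is the primary outcome and duration of admission is a secondary outcome (SAP 6.1). The trial is powered for a large mortality difference, the feasibility deaths came early, and Protocol 1.1 states that "KMC also reduces duration of hospitalisation".

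A baby who dies on day 2 cannot receive a treatment or investigation that would have come on day 6. If more control babies die early, a smaller percentage of controls will have received later-accruing care even when staff treat every living, admitted baby identically. Earlier discharge in the intervention arm pushes the other way.

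At stake is how this table is read in an unblinded trial. A low p-value may reflect survival or stay rather than unequal care, and a genuine imbalance opposite in direction to the artefact may be hidden.

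**Working it through.** **1. Reproduce the plan's figure.** SAP 3.3 states: "A total of 392 participants (1:1 ratio) were required to detect a 30% relative reduction in the primary outcome (power 80%, alpha=0.05". The control-arm rate used there is 48%, lowered from the 56% seen in the feasibility study. Intervention mortality is 0.48 × 0.70 = 0.336, a difference of 0.144, with mean 0.408.

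- Uncorrected n per arm = [1.96√(2 × 0.408 × 0.592) + 0.8416√(0.48 × 0.52 + 0.336 × 0.664)]² / 0.144² = 181.7.
- With continuity correction: (181.7/4) × [1 + √(1 + 4/(181.7 × 0.144))]² = 195.3, so 196 per arm and 392 in total. This matches for a two-sided 5% test.

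**2. Inputs for the check.**

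- From the documents: 196 per arm; mortality 48% vs 33.6%; death timing from Protocol 1.1, "median age at time of death 3d 2h and 71% (10/14) of all deaths occurred within the first week of admission".
- Assumed: enrolment at about 12h of age; mean survivor stay 14 days in both arms, or 21 (control) vs 14 (intervention); a rate of first receipt **identical in both arms**, between 0.1 and 5 per day, starting at enrolment or three days later; babies independent.
- A Weibull for age at death (shape 0.315, scale 1.60 days), conditional on being alive at enrolment, matches the median of 3d 2h and 10/14 deaths by day 7. Mean time from enrolment to death is then 5.35 days.

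**3. Time at risk.** Mean days in the window = mortality × 5.35 + (1 − mortality) × survivor stay.

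- Stay 14 vs 14: control 0.48 × 5.35 + 0.52 × 14 = 9.8; intervention 0.336 × 5.35 + 0.664 × 14 = 11.1.
- Stay 21 vs 14: control 0.48 × 5.35 + 0.52 × 21 = 13.5; intervention 11.1. The direction reverses.

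**4. One case by hand** (0.3 per day from enrolment, stay 14 vs 14).

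- Percentage received in an arm = mortality × (receipt among deaths) + (1 − mortality) × (receipt among survivors).
- With gamma-distributed stays (shape 4), receipt among survivors is 1 − (1 + 0.3 × 14/4)⁻⁴ = 0.943.
- The simulated control figure of 74.8% implies receipt among deaths of (0.748 − 0.52 × 0.943)/0.48 = 0.54.
- Intervention: 0.336 × 0.54 + 0.664 × 0.943 = 0.807, against 80.9% simulated.
- With equal stay the gap is the mortality difference times the difference in receipt: 0.144 × (0.943 − 0.54) = 0.058, about 6 points.

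**5. Simulation at 48% vs 33.6% mortality** (1,500 trials per row; Monte Carlo standard error near 5% is √(0.05 × 0.95/1500) = 0.6 points). Cells show % received, control vs intervention, then the share of trials with Fisher p<0.05.

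| Identical care in both arms | Stay 14 vs 14 | Stay 21 vs 14 |
|---|---|---|
| 5/day from enrolment (median wait about 3h) | 96.1 vs 97.2; 5% | 96.1 vs 97.3; 5% |
| 1/day from enrolment | 87.8 vs 91.4; 17% | 87.9 vs 91.5; 18% |
| 0.3/day from enrolment | 74.8 vs 80.9; 27% | 76.7 vs 80.8; 13% |
| 0.1/day from enrolment | 51.6 vs 57.0; 14% | 57.7 vs 57.2; 4% |
| 1/day from three days after enrolment | 69.5 vs 77.9; 42% | 71.0 vs 77.8; 29% |
| 0.3/day from three days after enrolment | 60.0 vs 68.2; 35% | 64.4 vs 68.1; 10% |

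A separate run with daily chances of 2–20% gave 7–24% with an 18-day stay in both arms, and 4–9% with 18 vs 14 days.

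**6. Controls on the mechanism.**

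- Equal mortality (48%) and equal stay: Fisher rejects in 3–5%, so unequal time at risk is the cause.
- Equal mortality, stay 21 vs 14: up to 19%, with the opposite sign (0.1/day: 57.7% vs 51.8%).
- Smaller effect, 48% vs 41%, equal stay: 3–10%.
- First receipt analysed per patient-day at risk: 3.5–6.5% in every row of the table, under both stay assumptions.

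**The case against.** Much of the other side's case stands.

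- **Coding.** The SAP does not say that indicators are coded as ever received. That is the natural reading of receipt shown as counts and percentages with Fisher's test, but 5.6 gives no derivations, and its continuous summaries could in principle be per-day measures. Totals accumulated over the stay would still be cut short by death and discharge.
- **Prompt care.** A reader might infer that the arm with more early deaths has less chance to receive anything at all. The documents do not support that. Oxygen, IV fluids and IV antibiotics are standard management already during screening (Protocol 5.3.2), and necessary procedures and medications come before allocated care begins (Protocol 5.7). Care of that kind differs by about 1 point, with no excess of rejections.
- **Offsetting discharge.** Earlier discharge in the intervention arm can shrink, cancel or reverse the gap. No single direction can be claimed.
- **Certainty.** A reader might also infer that a mortality benefit by itself produces significant differences in care. Even in the worst row, 58% of trials show none for that indicator.
- **Other safeguards.** This table is not the only protection. Protocol 3.5 also provides for discrepancies between arms to be identified prospectively and acted on, and compliance was monitored daily (SAP 3.1.4 and 5.6). Time to death and duration of admission are reported by arm, so an alert reader could see unequal exposure.

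None of this supplies a denominator. Prospective correction during the trial does not make the end-of-trial test interpretable, and reporting survival and stay elsewhere does not adjust the percentages in this table.

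**Conclusion.** The point holds for care that starts or accrues after the first days. For such care, the comparison in SAP 5.6 mixes how babies were treated with how long they remained alive and admitted.

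At design mortality and equal survivor stay, the false-positive rate per indicator is about 7–27% for care accruing from enrolment and up to about 42% for care starting on day 3, against about 5% for prompt care. With survivor stay of 21 vs 14 days it is about 4–13% for slowly accruing care (0.1–0.3 per day), but still 18% at 1 per day from enrolment and 29% for care at that rate starting on day 3. If mortality is equal and only stay differs, the bias runs the other way, with up to 19% rejection.

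Mortality, sample size and death timing come from the documents, the timing from only 14 deaths. Stay, receipt rates and age at enrolment are assumptions, so the figures show a plausible range, not a forecast. The distortion is small if the arms turn out alike in mortality and stay.

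A reader might go further and infer that the mortality result is compromised. It is not: no primary or secondary estimate depends on 5.6. The damage is limited to a supporting check on co-interventions, but in an unblinded trial that check should be interpretable.

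**What to change.** In SAP 5.6:

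1. Compare admission-care indicators over a fixed early window after enrolment, for example the first 24h and 72h.
2. Compare later treatments and investigations as rates per baby-day alive in hospital, using a Poisson model with log time at risk as offset and allowance for twin clustering. Twins share an arm (SAP 3.2), which Fisher's and t tests ignore.
3. Report time at risk by arm beside the table.

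The cost is SAP wording and derivation of a denominator. Treatments are recorded prospectively (Protocol 3.5), as are the date and time of discharge or death (Protocol 6.1.4). One limit needs handling: study reviews are daily only until KMC-unit admission and weekly after that (Protocol 6.1.2). If daily treatment records are not available on the KMC unit, restrict the rates to neonatal-unit days and say so. The remaining drawback is that the rates describe care among babies still alive and admitted, and the table should state this.
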